### 16.8 Schedule of Assessments

Study Period	Screening		Lead-in	Treatment						Follow-up	
	1	2		3	4	5	6	7	8	9	10
Week	Up to -6 weeks		-1	NA	1	2	4	8	12	16	24
Study Day	≤ 63 days A before Day 1	-21	-7	1	8	15	29	57	85	113	169
Visit Window (Days)	NA	± 7	± 4	NA	± 3	± 3	± 3	± 5	± 5	± 7	± 7
Informed consent / IRT registration	X										
Eligibility criteria	X	X									
Randomization criteria B			X	X							
Medical history	X										
Demographics	X										
Virology testing	X										
Pregnancy test (FCBP) C	X		X	X			X	X	X	X	X
Physical examination D		X	X	X	X	X	X	X	X	X	X
Vital signs E	X	X	X	X	X	X	X	X	X	X	X
Height and weight F	X		X	X	X	X	X	X	X	X	X
12-lead electrocardiogram G	X		X	X	X	X	X	X	X	X	X
Echocardiogram H	X										
Troponin-I and BNP	X		X	X	X	X	X	X	X	X	X
Coagulation (PT / INR and aPTT)	X										
HbA1c	X			X						X	X
Hematology and biochemistry	X	X I	X	X	X	X	X	X	X	X	X
Urinalysis	X			X							
Timed 24-hour urine J	X				X				X		
First morning void urine K			x3	x3		x3	x3	x3	x2	x3	x3
Morning midstream urine L			X	X			X	X		X	

Study Period	Screening		Lead-in	Treatment						Follow-up	
	1	2		3	4	5	6	7	8	9	10
Week	Up to -6 weeks		-1	NA	1	2	4	8	12	16	24
Study Day	≤ 63 days A before Day 1	-21	-7	1	8	15	29	57	85	113	169
Visit Window (Days)	NA	± 7	± 4	NA	± 3	± 3	± 3	± 5	± 5	± 7	± 7
SC normal saline test infusion		X									
Randomization				X							
IRT IP assignment				X			X	X	X		
IP administration M				IV and SC			SC	SC	SC		
Serum PK sampling N				X	X	X	X	X	X	X	X
Local tolerability assessment				X	X	X	X	X	X	X	
Adverse events	From ICF Signature through Last Visit										
Concomitant medications	From ICF Signature through Last Visit										
Immunogenicity				X			X	X		X	
Biomarker sample (blood) O			X	X			X	X		X	

ACR = albumin-to-creatinine ratio; aPTT = activated partial thromboplastin time; BNP = b-type natriuretic peptide; BP = blood pressure; EOS = End of Study; FCBP = female subjects of childbearing potential; HbA1c = hemoglobin A1c; ICF = informed consent form; IMP = investigational medicinal product; INR = international normalized ratio; PT = prothrombin time; IP = investigational product; IRT = interactive response technology; IV = intravenous(ly); PK = pharmacokinetic; SC = subcutaneous(ly); VEGF = vascular endothelial growth factor.

**Notes to the Schedule of Assessments:**

- A:** Screening Visit 1 should be performed within 6 weeks before Screening Visit 2.
- B:** Randomization criteria will include evaluations of BP, serum creatinine, and troponin.
- C:** A serum pregnancy test will be performed at Screening for FCBP; serum or urine pregnancy tests will be performed at all other indicated visits.
- D:** A comprehensive physical examination will be performed at Visit 2 (Day –21) and at EOS. An abbreviated physical examination will be performed for all other indicated visits.
- E:** Vital signs include BP (systolic and diastolic), temperature, and pulse. Blood pressure measurements should be taken in triplicate before all other assessments. Vital signs in general will be collected before any blood samples that are collected at the same time point. At Visit 2 (Day –21), BP will be the only vital sign collected. Instructions for measuring BP will be provided in the Manual of Operations. At Visit 4 (Day 1), vital sign measurements will be taken predose, at 30, 60, and 120 minutes ( $\pm$  15 minutes) after the first IV dose of IP (before the first SC dose of IP) is administered, then at 30 and 60 minutes ( $\pm$  15 minutes) after SC dosing.
- F:** Height will be measured at Screening only.
- G:** Electrocardiograms must be performed in triplicate before any blood samples that are collected at the same time point.
- H:** A local assessment of echocardiogram will be performed during Screening unless an echocardiogram was performed for non-study-related reasons within 3 months before Screening.
- I:** At Visit 2 (Day –21), a blood sample will be collected for determination of serum creatinine only.
- J:** A timed 24-hour urine sample will be collected to assess eligibility (ACR) at Screening (Baseline), and to measure CSL346 levels in urine at subsequent indicated visits.
- K:** Subjects will collect urine from their first morning void on 3 consecutive days (2 consecutive days for Visit 9) leading up to and including the morning of each indicated visit.
- L:** Morning midstream urine samples will be collected to evaluate exploratory biomarkers and will also be stored for future research analyses.
- M:** Specific instructions for administration of IP are provided in the IMP Handling Manual. At Visit 4 (Day 1), an initial loading dose of IP will be administered by IV, followed at least 2 hours (but no more than 6 hours) later by the subject's normal prescribed dose by SC infusion. Subsequent doses of IP will be administered by SC infusion.
- N:** Serial blood samples for PK will be collected at Visit 4 (Day 1) predose, at 30 ( $\pm$  5 minutes), 60 ( $\pm$  10 minutes), and 120 ( $\pm$  10 minutes) minutes after the first IV dose of IP (before the first SC dose of IP) is administered, then after the final vital signs measurement. Single PK samples will also be collected at all subsequent visits (before treatment on SC dosing days).

On biomarker blood sample collection days, subjects will arrive following a minimum 6-hour fast. Blood biomarker samples will be collected to evaluate pharmacodynamic and exploratory biomarkers and will also be stored for future research analyses.

### 16.9 Directionality of One-sided Tests

Since treatment comparisons in this study are based on one-sided tests, we need to designate the direction of these tests. Directionality and method for calculating one-sided p-value from the two-sided p-value is specified in the table below.

Parameter Name	Better (Lower or Higher)	Comment	One sided p-value calculated as:
Biomarkers of Lipid Metabolism: Total Cholesterol	Lower	Compared to PBO	estimate < 1 p-one sided=p/2 estimate >= 1 p-one sided=1-p/2
Biomarkers of Lipid Metabolism: Triglycerides –	Lower	Decreased triglycerides in the fed state, compared to PBO could indicate activity, but in fasted samples, no change would be predicted.	estimate < 1 p-one sided=p/2 estimate >= 1 p-one sided=1-p/2
Biomarkers of Lipid Metabolism: HDL –	Higher	Compared to PBO	estimate < 1 p-one sided=1-p/2 estimate >= 1 p-one sided=p/2
Biomarkers of Lipid Metabolism: LDL –	Lower	Compared to PBO	estimate < 1 p-one sided=p/2 estimate >= 1 p-one sided=1-p/2
Biomarkers of Lipid Metabolism: (Fasting) Glycerol –	Higher	Smaller (or no) increase in fasting glycerol, NEFA, ketones compared to PBO could indicate activity	estimate < 1 p-one sided=1-p/2 estimate >= 1 p-one sided=p/2
Biomarkers of Lipid Metabolism: (Fasting) NEFA –	Higher		estimate < 1 p-one sided=1-p/2 estimate >= 1 p-one sided=p/2
Biomarkers of Lipid Metabolism: (Fasting) Ketones –	Higher		estimate < 1 p-one sided=1-p/2 estimate >= 1 p-one sided=p/2
Biomarkers of VEGF Family: Urinary VEGF-A	Lower	Decrease in total VEGF-A compared to PBO could indicate activity	estimate < 0 p-one sided=p/2 estimate >= 0 p-one sided=1-p/2
Biomarkers of VEGF Family: Urinary Soluble VEGF-R1	Lower	Decrease in total VEGF-R1 compared to PBO could indicate activity	estimate < 0 p-one sided=p/2 estimate >= 0 p-one sided=1-p/2
Biomarkers of Tubular Injury: KIM-1	Lower	Compared to PBO	estimate < 0 p-one sided=p/2 estimate >= 0 p-one sided=1-p/2

Biomarkers of Tubular Injury: NGAL	Lower	Compared to PBO	estimate < 0 p-one sided=p/2 estimate >= 0 p-one sided=1-p/2
Biomarkers of Tubular Injury: MCP-1	Lower	Compared to PBO	estimate < 0 p-one sided=p/2 estimate >= 0 p-one sided=1-p/2
Biomarkers of Tubular Injury - EGF	Higher	Compared to PBO	estimate < 0 p-one sided=1-p/2 estimate >= 0 p-one sided=p/2
Biomarkers of Tubular Injury: Clusterin	Lower	Compared to PBO	estimate < 0 p-one sided=p/2 estimate >= 0 p-one sided=1-p/2
Circulating Biomarker of Inflammation: sTNFR1	Lower	Compared to PBO	estimate < 0 p-one sided=p/2 estimate >= 0 p-one sided=1-p/2
ACR	Lower	Compared to PBO	estimate < 1 p-one sided=p/2 estimate >= 1 p-one sided=1-p/2
eGFR	Higher	Compared to PBO	estimate < 0 p-one sided=1-p/2 estimate >= 0 p-one sided=p/2
Serum Creatinine	Lower	Compared to PBO	estimate < 0 p-one sided=p/2 estimate >= 0 p-one sided=1-p/2
Blood pressure	Lower	Compared to PBO	estimate < 0 p-one sided=p/2 estimate >= 0 p-one sided=1-p/2
Weight	Lower	Compared to PBO	estimate < 0 p-one sided=p/2 estimate >= 0 p-one sided=1-p/2
HbA1C	Lower	Compared to PBO	estimate < 0 p-one sided=p/2 estimate >= 0 p-one sided=1-p/2
Fasting glucose	Lower	Compared to PBO	estimate < 0 p-one sided=p/2 estimate >= 0 p-one sided=1-p/2

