# **1 Modification History**

Version	Effective Date	Author of Modification	Summary of Change
Draft 1.0	30Sep2020	PPD	N/A – First Version
Draft 2.0	28Oct2020	PPD	Implementation of sponsor review comments
Draft 3.0	07Dec2020	PPD	Implementation of sponsor review comments
Final 1.0	11Dec2020	PPD	N/A
Draft of Final 1.1	16Jul2021	PPD	Alignment with Protocol Amendment 2 including; 
 
• Added potential inclusion of subjects with estimated glomerular filtration rate between > 20 and < 45 mL/min/1.73m^2 subject to endorsement by the Independent Data Monitoring Committee
 
• Changed the adverse events of special interest criteria for increases in albumin-to-creatinine ratio
 
• Added sensitivity analysis employing multiple imputation for missing data
 
• Added sensitivity analysis to reflect the impact of novel coronavirus 2019
 
• Added Screened Analysis Set
 
• Added Interim Analysis for decision making
 

Draft of Final 1.2	02Dec2021	PPD	Implementation of sponsor review comments for alignment with Protocol Amendment 2

Version	Effective Date	Author of Modification	Summary of Change
Final 2.0	10Dec2021	PPD	N/A
Final 3.0	29Sep2022	PPD	
 
• Summaries of Prior and Concomitant medications will be based on either the Safety Analysis Set or the Per Protocol Analysis Set.
 
• Added Appendix table showing directionality of one-sided testing
 
• Clarification regarding normalization of urinary biomarkers
 
• Specification of non-SI units for particular parameter reporting
 
• Correction of estimand
 
• Clarifications and updates regarding Per Protocol Analysis Set
 
• Baseline for multiple parameters defined as the average of two measurements
 
• Sentence added indicating total dose received (mg/kg) will be provided with study data
 
• Specification for KIM-1, NGAL, EGF (new parameter), and MCP-1 analyses to be performed for the PP Analysis Set
 
• Removal of VEGF-B since it will not be available
 

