#### 4.1.4 Exploratory Endpoints

The exploratory endpoints for this study are:

1. Changes from Baseline to each assessment in fasting values for the following PD biomarkers:
  - biomarkers of lipid metabolism including but not limited to circulating total cholesterol, triglycerides, high density lipoproteins (HDL), low density lipoproteins (LDL), glycerol, non-esterified fatty acids (NEFA), and ketones;
  - biomarkers of glycemic control including but not limited to fasting glucose and hemoglobin A1c (HbA1c);
  - novel biomarkers, including but not limited to soluble tumor necrosis factor receptor 1 (sTNFR1), and urinary VEGF-A, soluble VEGF receptor 1 (VEGF-R1), kidney injury molecule-1 (KIM-1), neutrophil gelatinase-associated lipocalin (NGAL), epidermal growth factor (EGF), clusterin, and monocyte chemoattractant protein-1 (MCP-1).
2. Concentration of CSL346 found in urine at Week 1 (Visit 5) and Week 12 (Visit 9).
3. Number (percent) of patients who regress from macroalbuminuria to microalbuminuria or normoalbuminuria, or from microalbuminuria to normoalbuminuria at Week 16 (Visit 10) compared to Baseline.

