### **10.3 Analysis of Other Secondary Endpoints**

Biomarkers of lipid metabolism, glycemic control and novel biomarkers of kidney function as well as weight will also employ a model similar to the primary endpoint except for the

concentration of CSL346 in urine. The analysis for continuous endpoints is an MMRM analysis of change from baseline to each post-baseline measurement (Weeks 4, 8 and 16). The model will include treatment, stratification related to the concomitant use of SGLT2i, visit (as a categorical factor), and interactions between visit and each of the other model terms, as well as the corresponding baseline measurement as a covariate (refer to [Section 16.1](#) for respective SAS code). Treatment comparisons of interest will be similar to that of the primary endpoint. Lipid parameters will be natural log transformed prior to analysis.

Urinary biomarkers will be normalized for urine creatinine. These urinary biomarkers include urinary VEGF-A, soluble VEGF receptor 1 (VEGF-R1), kidney injury molecule-1 (KIM-1), neutrophil gelatinase-associated lipocalin (NGAL), clusterin, and monocyte chemoattractant protein-1 (MCP-1) and epidermal growth factor (EGF). Normalization is performed by dividing the urinary biomarker by urine creatinine collected at the midstream morning void taken the same day as the urinary biomarker. Normalized urinary biomarkers should be reported in units of pg/ $\mu$ g. To obtain these units, first convert urinary creatinine from units of mg/dL to units of  $\mu$ g/mL by multiplying by 10. Then divide the urinary biomarker (pg/mL) by urinary creatinine ( $\mu$ g/mL) to get normalized results with units of pg/ $\mu$ g.

A repeated measures analysis of covariance model will be employed to analyze the concentration of CSL346 in urine, collected at Day 1, Day 8, and Day 85. The repeated measures analysis of covariance model will include terms for treatment, baseline as a covariate and SGLT2i use.

All analyses for biomarker will be performed on the PD Analysis Set. Analyses for KIM-1, NGAL, EGF and MCP-1 will be performed in addition for the PP Analysis Set. Analyses for urine CSL346 concentration will be performed on the ITT Analysis Set.

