## 16 Appendices

### 16.1 SAS Code

SAS code for MMRM analysis

```
Ods graphics on;
Proc mixed data=data_set method=reml plots=residualpanel;
  Class treatment visit patient sglti_yn;
  Model chglnacr =treatment visit baseline sglti_yn
  treatment*visit sglti_yn*visit baseline*visit / alpha=0.20 cl
  ddfm=kr covb solution;
  Repeated visit / type=un subject=patient r rcorr;

* *** Estimate for treatment difference at 2 weeks *** *;
  Estimate "CSL08 vs. PBO at 2 weeks" treatment 1 0 -1
  treatment*visit 1 0 0 0 0 0      0 0 0 0 0 0      -1 0 0 0 0 0 / CL
  alpha=0.2;
  ESTIMATE "CSL16 vs. PBO at 2 weeks" treatment 0 1 -1
  treatment*visit 0 0 0 0 0 0      1 0 0 0 0 0      -1 0 0 0 0 0 / CL
  alpha=0.2;
  ESTIMATE "CSL vs. PBO at 2 weeks" treatment 0.5 0.5 -1
  treatment*visit 0.5 0 0 0 0 0      0.5 0 0 0 0 0      -1 0 0 0 0 0 / CL
  alpha=0.2;

* *** Estimate for treatment difference at 16 weeks *** *;
  Estimate "CSL08 vs. PBO at 16 weeks" treatment 1 0 -1
  treatment*visit 0 0 0 0 1 0      0 0 0 0 0 0      0 0 0 0 -1 0 / CL
  alpha=0.2;
  ESTIMATE "CSL16 vs. PBO at 16 weeks" treatment 0 1 -1
  treatment*visit 0 0 0 0 0 0      0 0 0 0 1 0      0 0 0 0 -1 0 / CL
  alpha=0.2;
  ESTIMATE "CSL vs. PBO at 16 weeks" treatment 0.5 0.5 -1
  treatment*visit 0 0 0 0 0.5 0      0 0 0 0 0.5 0      0 0 0 0 -1 0 / CL
  alpha=0.2;

  Lsmmeans treatment treatment*visit / diff cl;
run;
Ods graphics off;
```

Where:

- chglnacr is the repeated measure of change in log ACR collected at Weeks 2, 4, 8, 12, 16 and 24;
- treatment takes on three levels (CSL346 8 mg/kg, CSL346 16 mg/kg and placebo)

- sglt2i\_yn is the stratification variable associated with the presence or absence of a concomitant SGLT2i at entry into the trial;
- baseline is the baseline log ACR used as a covariate in the model;
- visit is the time variable;

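### SAP 16.9: the comment on fasting glycerol, NEFA and ketones points the opposite way from their *Higher* label and one-sided p-value rule; SAP 4.1.6 also words eGFR against its 16.9 direction

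*SAP*

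**What the plan says.** SAP 16.9 opens by stating its purpose: "Since treatment comparisons in this study are based on one-sided tests, we need to designate the direction of these tests". For each parameter its table gives whether lower or higher is better, a comment, and the conversion from a two-sided to a one-sided p-value. The modification history records it under Final 3.0: "Added Appendix table showing directionality of one-sided testing".

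Fasting glycerol, NEFA and ketones are each labelled *Higher*, each with the rule "estimate < 1 p-one sided=1-p/2 estimate >= 1 p-one sided=p/2". The one comment for this block stands in the glycerol row and names all three markers: "Smaller (or no) increase in fasting glycerol, NEFA, ketones compared to PBO could indicate activity". The comment cells for NEFA and ketones are empty.

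SAP 10.3 sets the scale: "Lipid parameters will be natural log transformed prior to analysis". The markers are among the exploratory endpoints of SAP 4.1.4 ("glycerol, non-esterified fatty acids (NEFA), and ketones").

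On eGFR, SAP 4.1.6 words the key secondary hypothesis as one about decreases and lists eGFR together with serum creatinine and blood pressure. SAP 10.2 says these endpoints are tested in the same way as the primary endpoint, whose alternative in SAP 4.1.5 is a ratio below 1. SAP 16.9 labels eGFR *Higher*.

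**The concern.** A one-sided test is credible only if its direction is fixed before the data are seen. For these three markers the table that fixes it gives two directions: the comment describes activity as a smaller rise than placebo, while the label and formula reward a larger one. If this survives unblinding, a result either way can be presented as the predicted one, by citing the comment or the label.

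If the comment states the real hypothesis, an effect in the expected direction cannot be declared significant, however large it is. For eGFR, a reader of 4.1.6 and 10.2 could conclude that the plan tests for a fall, which is not what 16.9 does.

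**Working it through.** **1. Translate the comment to the analysis scale.** Lipid parameters are log transformed (SAP 10.3) and the null value in the three rows is 1 (SAP 16.9), so the back-transformed estimate is a CSL346/placebo ratio. A smaller increase than placebo is a ratio below 1.

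**2. Apply the printed rule.** For an estimate below 1, one-sided p = 1 − p/2. Since p ≤ 1, this is at least 0.50 and can never reach 0.10. Under a *Lower* rule it would be p/2.

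| Two-sided p, ratio below 1 | *Higher* rule, as printed | *Lower* rule |
|---|---|---|
| 0.10 | 0.95 | 0.05 |
| 0.01 | 0.995 | 0.005 |

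The label and formula agree with each other: the printed rule is exactly the upper-tail p-value. The comment is what disagrees with both.

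**3. Compare with the rest of the table.** Three other comments in 16.9 describe a possible sign of activity: triglycerides, urinary VEGF-A and urinary soluble VEGF-R1. Each describes a decrease and each row is labelled *Lower*. Only the glycerol/NEFA/ketones comment runs against its label.

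**4. Count the p-values.** For the combined contrast at Week 16 there are 3. If every post-baseline visit (Weeks 4, 8, 16; SAP 10.3) and every contrast (8 mg/kg, 16 mg/kg, combined; SAP 16.1) were reported, there would be 3 × 3 × 3 = 27.

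**5. Size of the loss if the comment is intended.** The documents give no SD or target effect for these markers, so the effect is put in SD units and this is an illustration only. Inputs from SAP 4.4: design difference 0.315, SD 0.65, 94 completers (47 per group), one-sided alpha 0.10.

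First, the plan's own figures. Degrees of freedom = 92, critical t = 1.291, SE = 0.65 × √(2/47) = 0.134. The critical difference is 1.291 × 0.134 = 0.173 and the power by noncentral t is 85.5%, which match the stated 0.173 and 85%.

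Now let a marker have a true effect of d SD towards a ratio below 1, with noncentrality −d × √(47/2):

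| d | Noncentrality | P(significant), *Lower* | P(significant), *Higher* |
|---|---|---|---|
| 0.315/0.65 = 0.4846 | −2.349 | 0.855 | 0.00015 |
| 0.20 | −0.970 | 0.376 | 0.0123 |

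For 40 to 50 per group at d = 0.4846, the figures run from 0.809 to 0.871 (*Lower*) and from 0.0003 to 0.0001 (*Higher*).

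**6. eGFR, side by side.** SAP 4.1.6 puts eGFR under decreases. SAP 10.2 ties its testing to the primary endpoint without referring to 16.9 for direction. SAP 16.9 assigns p/2 when the eGFR difference is zero or above. If 16.9 is followed, no eGFR p-value changes.

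**The case against.** The strongest reply is that the operative rule is clear. The columns that set direction and calculation agree for all three markers, a programmer will follow them, and the comment is tentative and carries no rule. Comments in this table also need not state the tested alternative: the triglycerides row is *Lower*, although its comment expects no change in fasted samples. This stands as far as programming goes. It does not settle the intended direction, because no text ranks the label above the comment, and predicting no change is not the same as predicting the opposite direction.

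On eGFR, the primary test is described as one of superiority at one-sided 0.10. Testing eGFR identically can therefore mean superiority, which for eGFR is higher, and the 4.1.6 phrase could be read as governing serum creatinine only. This largely stands, and the eGFR point is editorial.

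On size, the power contrast shows only that a one-sided test has almost no power in the wrong tail. It borrows the ACR design effect and completer number for markers analysed in the PD Analysis Set, and 27 is an upper bound. All of that is fair. In addition, the two-sided p allows a reader to recover either tail, and SAP 10 says exploratory biomarkers go into a separate report without making clear how that fits with 10.3. These points limit the consequence but leave the contradiction in place.

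**Conclusion.** The concern holds, as a minor point. The table that designates test directions contradicts itself for fasting glycerol, NEFA and ketones, and the documents do not resolve it. If the comment is the intended hypothesis, the one-sided p-values for the three markers (3 at Week 16 for the combined contrast, at most 27) are computed in the wrong tail. If the label is intended, the tests are right and the loss is zero. The power figures rest on an assumed effect in SD units and an assumed 47 per group.

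Estimates and the 80% confidence intervals from the SAP 16.1 template are unaffected, so a ratio below 1 would still be visible. The primary ACR test is also unaffected. For eGFR only the hypothesis wording needs correcting.

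**What to change.** Before unblinded outputs are read, the sponsor should confirm the intended direction for the three markers and align label, comment and rule in SAP 16.9, in one of two ways:

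- set the three rows to *Lower*, so that an estimate below 1 gives p/2 and an estimate of 1 or above gives 1 − p/2; or
- keep *Higher* and its rule, and correct the comment.

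In SAP 4.1.6, take eGFR out of the list of decreases. In SAP 10.2, state that model, contrast and alpha follow the primary endpoint and that 16.9 gives the direction of each test. Leave the eGFR row in 16.9 as it is. If outputs have already been read, record the resolution in the clinical study report, as SAP Section 3 provides for deviations.

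The cost is a few words in three SAP sections and at most three lines of programming. No new data are needed.

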## 16.10 Non-SI Units

Certain parameters should be reported in non-SI units (conventional units). These parameters, along with the specified units for reporting, are shown in the table below.

Parameter	Conventional Units	SI Units	Conversion Factor
Albumin-creatinine ratio	mg/g	mg/mmol	To convert ACR in mg/mmol to mg/g, divide by 0.113
Creatinine	mg/dL	μmol/L	To convert Creatinine in μmol/L to mg/dL, divide by 88.4
HbA1c	%	HbFract	To convert HbA1c in HbFract to %, multiply by 100
Total cholesterol	mg/dL	mmol/L	To convert Total cholesterol in mmol/L to mg/dL, divide by 0.0259
HDL cholesterol	mg/dL	mmol/L	To convert HDL cholesterol in mmol/L to mg/dL, divide by 0.0259
LDL cholesterol	mg/dL	mmol/L	To convert LDL cholesterol in mmol/L to mg/dL, divide by 0.0259
Triglycerides	mg/dL	mmol/L	To convert Triglycerides in mmol/L to mg/dL, divide by 0.0113

